2.2 Patient disposition, demographics and other baseline characteristics

Analyses will be based on the FAS.

2.2.1 Patient disposition

The number and percentage of subjects in the FAS who completed study periods and who discontinued the study prematurely (including the reason for discontinuation) after Week 60E1 will be presented for each treatment group and all subjects.

For each protocol deviation, the number and percentage of subjects for whom the deviation applies will be tabulated.

2.2.2 Demographics and baseline characteristics

Demographic and other baseline data, including disease characteristics, will be summarized by treatment groups for FAS.

- Gender, age, race, ethnicity, weight, height, BMI (Body Mass Index), disease duration and smoking status.
- •

- Number (%) of patients with use of DMARDs (split by type, e.g. hydroxychloroquine, methotrexate, azathioprine, prednisone or other corticosteroid) at baseline.
- •
- Number (%) of patients with history of prior biologics treatment for SjS.

Relevant medical histories and current medical conditions at baseline will be coded according to MedDRA dictionary version that is current at time of database lock and summarized by system organ class and preferred term for each treatment group.

Unless otherwise specified, summary statistics will be presented for continuous variables for each treatment group and total. The number and percentage of subjects in each category will be presented for categorical variables for each treatment group and total.

2.2.3 Medical history

Any condition entered on the *Relevant medical history / current medical conditions* CRF (including family history, concomitant asthma diagnosis, food allergies etc.) will be coded using the MedDRA dictionary. They will be summarized by System Organ Class (SOC) and Preferred Term (PT) of the MedDRA dictionary.

2.3 Treatments (study treatment, rescue medication, concomitant therapies, compliance)

2.3.1 Study treatment / compliance

The analysis of study treatment data will be based on the safety set.

Duration of exposure will be defined as the time from first dose of study medication to the last dose date plus 14 days.

For subjects who completed treatment, there is a visit window of \pm 5 days for the 14 days. For subjects who discontinued treatment, the EoT disposition date is the last assessment date in treatment period. Therefore, the EoT visit was not considered ideal for the end of exposure calculation and the current exposure calculation method is proposed:

Duration of exposure (days) = (last dose date + 14 days) - first dose date +1

Duration of exposure (weeks) = duration of exposure (days) / 7

The number and percentage of patients in SAF who are exposed to study treatment for prespecified time intervals (every two weeks) will be summarized for the overall study. Patients who receive any wrong study medications will be listed.

2.3.2 Prior, concomitant and post therapies

Concomitant treatments and prior medications entered into the database will be coded using the World Health Organization (WHO) Drug Reference List, which employs the Anatomical Therapeutic Chemical classification system (ATC).). Prior and concomitant treatments will be

summarized by treatment group for the safety set unless otherwise specified. Concomitant treatments will be displayed for the treatment period.

Medications will be presented by ATC code and preferred term. ATC codes will be displayed in alphabetical order, and grouped by *anatomical main group* (the 1st level of the ATC codes). Tables will also show the overall number and percentage of subjects receiving at least one drug of a particular ATC code and at least one drug in a particular anatomical main group.

Prior medications are defined as drugs taken and stopped prior to the first dose of study treatment in core study. Any medication given at least once between the day of first dose of study treatment during extension period, and the last dose during extension period will be a **concomitant** medication, including those which were started pre-week 60 and continued into the extension treatment period. Any medication given at least once between the day of first dose of study treatment, and the last dose during core study period, which is stopped before end of extension study will be a **concomitant** medication only for core study.

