6.2 Other treatment(s)

Participants experiencing disease signs and symptoms may receive short-term symptomatic care with over-the-counter, anti-inflammatory/analgesic agents such as nonsteroidal anti-inflammatory drugs (NSAID) and paracetamol. Participants whose SjS disease signs and symptoms are not adequately controlled by symptomatic care, and/or who suffer from more severe SjS disease manifestations not suitable for such treatment, may receive rescue therapy with corticosteroids, if determined by the Investigator to be medically necessary ([Section 6.2.3](#)).

There is currently no consensus on the definition of flare in SjS. With reference to the recently completed JOQUER trial in pSS ([Gottenberg et al 2014](#)) that reported 12 flares among 120 patients during 12 months, it is conceivable that < 10% of all patients in the current iscalimab trial will experience a deterioration (or ‘flare’) that warrants treatment escalation. Treatment escalation would, for example, be increasing the steroid dose, or introducing de novo an immunosuppressant agent like azathioprine. Participants who require escape treatment (other than allowed rescue medications – see [Section 6.2.3](#)) must be discontinued from study medication, enter the safety follow-up period and follow the local standards for treatment of SjS worsening. In the absence of consensus guidelines for treatment of systemic manifestations in SjS, it is recommended to consult the SLE treatment guidelines as far as they pertain to the respective organ involvement observed in the trial (for example renal, nervous system or skin vasculitis).

Any medication used to treat Adverse Events (AE) must be recorded on the Case Report Form (CRF).

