12.3 Treatments

Analyses of treatment will be based on the SAF.

Study treatment:

The duration of exposure to study treatment will be summarized by treatment group. In addition, the number of participants with exposure of at least certain thresholds (e.g., any exposure, ≥ 2 weeks ≥ 4 weeks ≥ 6 weeks ≥ 8 weeks etc.) will be displayed.

Prior and concomitant medication:

Prior medications are defined as treatments taken and stopped prior to first dose of study treatment. Any medication given at least once between the day of first dose of randomized study treatment and the date of the last study visit will be a concomitant medication, including those which were started pre-baseline and continued into the period where study treatment is administered.

Prior and concomitant medications will be summarized in separate tables. Medications will be presented in alphabetical order, by Anatomical Therapeutic Classification (ATC) codes and grouped by anatomical main group. Tables will show the overall number and percentage of participants receiving at least one treatment of a particular ATC code and at least one treatment in a particular anatomical main group.

The number and percentage of participants receiving systemic therapies for pSS as prior and concomitant background medication will be presented separately by preferred term.

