12.4.2 Statistical model, hypothesis, and method of analysis

Only descriptive statistics will be provided, no inferential statistics will be conducted.

Adverse events:

Treatment emergent adverse events (TEAEs) will be summarized. Only primary paths within MedDRA will be considered for AE reporting. The definition for “treatment emergent” is as follows:

- Events started on or after the first dose of study treatment or events present prior to the first dose of study treatment but increased in severity based on preferred term;
- AEs observed four weeks after last study-drug administration will not be considered as treatment-emergent

AEs will be summarized by presenting, for each treatment group, the number and percentage of participants having any AE, having an AE in each primary system organ class and having each individual AE (preferred term). Summaries will also be presented for AEs by severity and for study treatment related AEs. If a participant reported more than one AE with the same preferred term, the AE with the greatest severity will be presented. If a participant reported more than one AE within the same primary system organ class, the participant will be counted only once with the greatest severity at the system organ class level, where applicable.

SAEs will also be summarized.

Separate summaries will be provided for deaths, SAEs, and other significant AEs leading to discontinuation.

All AEs including non-treatment emergent AEs will be listed.

Laboratory data:

The summary of laboratory evaluations will be presented for two groups of laboratory tests (hematology and serum chemistry). Descriptive summary statistics for the change from baseline to each study visit will be presented. These descriptive summaries will be presented by laboratory test and treatment group. Change from baseline will only be summarized for participants with both baseline and post-baseline values. For each parameter, the maximum change from baseline will be analyzed analogously. Number and percentage of participants with notable abnormalities will be summarized.

Vital signs:

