2.4 Safety analyses

All safety endpoints (i.e., adverse events, laboratory data, and vital signs in extension study will be summarized by treatment for all subjects of the safety set.

Adverse events (AEs)

All adverse events in extension study are summarized based on treatment emergent only. The definition for "treatment emergent" is as below:

TEAE includes all events up to the last dose date plus 14 weeks (98 days) or the end of the entire study period (including the safety follow-up period), whichever occurred earlier. A listing of all adverse events during the study will be produced, with those defined as TEAE for the study treatment period with "treatment emergent" flag displayed.

The number and percentage of patients with treatment emergent adverse event (TEAE) will be summarized for the following:

- by treatment, primary system organ class and preferred term
- by treatment, primary system organ class, preferred term and maximum severity
- by treatment, Standardized MedDRA Query (SMQ) and preferred term.

Summaries will also be provided for study treatment related adverse events, serious adverse events, treatment related serious adverse events, deaths, and adverse events leading to permanent discontinuation of study-drug.

If a particular AE 'severity' is missing, this variable will be listed as missing and treated as missing in summaries. If a subject reported more than one adverse event with the same preferred term, the adverse event with the greatest severity will be presented. If a subject reported more than one adverse event within the same primary system organ class, the subject will be counted only once with the greatest severity at the system organ class level, where applicable.

The most common adverse events reported ($\geq 5\%$ in any group for each preferred term in the table by PT or $\geq 5\%$ in any group for each SMQ table) will be presented in descending frequency according to its incidence in all subjects starting from the most common event.

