2.7 Interim analysis

There is no interim analysis planned for the study.

3 Change to protocol specified analyses

- New broader definition of TEAE than defined in the protocol

4 Appendix

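### The SAP ends the concomitant-medication window at the last extension dose, without declaring the change from the protocol, while TEAEs are counted for up to 98 days longer

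*SAP*

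**What the plan says.** **Medication window.** Protocol 12.3 treats as concomitant any drug given at least once between the first dose "and the date of the last study visit will be a concomitant medication". SAP 2.3.2 moves the end point: a drug given between the first extension dose "and the last dose during extension period will be a" concomitant medication. It adds: "Concomitant treatments will be displayed for the treatment period". Prior medications are those stopped before the first dose in the core study. Post therapies are named in the title of SAP 2.3.2 and in an imputation heading (SAP 4.1.3.2), but the visible text gives them no definition, window or table.

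**TEAE window.** Protocol 12.4.2 closes it four weeks after dosing: "AEs observed four weeks after last study-drug administration will not be considered as treatment-emergent". SAP 2.4 lengthens it: "TEAE includes all events up to the last dose date plus 14 weeks (98 days) or the end of the entire study period", whichever is earlier.

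**Declared changes.** The only entry in SAP Section 3 is "New broader definition of TEAE than defined in the protocol".

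**Escape treatment.** Under Protocol 6.2, participants who need escape treatment beyond the allowed rescue medication "must be discontinued from study medication, enter the safety follow-up period and follow the local standards for treatment of SjS worsening". Table 6-2 requires study drug to be stopped for other biologics, cyclophosphamide, oral cyclosporine and oral MMF.

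**The concern.** The protocol's medication window was long enough to cover its TEAE window. The SAP lengthened the TEAE window and shortened the medication window, and declared only the first change. In the stretch after the last dose, adverse events are counted by dose group but newly started drugs are not tabulated.

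That stretch is where escape immunosuppression can be expected to begin, because the protocol ties it to stopping study drug. The primary endpoint is the safety profile, and infection heads the list of risks in Table 4-1. Protocol 4.5 itself names MMF and prednisolone among the confounders of the one fatal case it describes. A reader of the extension tables could see an infection during follow-up with no sign that another immunosuppressant had been started first.

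**Working it through.** **Inputs.** Protocol schedule (Section 8, Table 8-1): Week 60E1 = Day 421, Week 106 (last dose) = Day 743, Week 108 = Day 757, Week 120 (last visit) = Day 841. SAP Table 2-1, counting from the first extension dose: Week 106 = Day 323, Week 120 = Day 421. Enrolled: 206 (SAP 1.1).

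**Step 1: reproduce the SAP's 98 days.** 14 × 7 = 98. Week 120 minus Week 106 is 841 − 743 = 98 on the protocol's day count and 421 − 323 = 98 on the SAP's. The figure reproduces exactly.

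**Step 2: compare the two pairs of windows for a completer.**

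| Rules | Medication window ends | TEAE window ends | Medication minus TEAE |
|---|---|---|---|
| Protocol 12.3 and 12.4.2 | last visit, Day 841 | last dose + 28, Day 771 | +70 days |
| SAP 2.3.2 and 2.4 | last dose, Day 743 | last dose + 98, Day 841 | −98 days |

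The protocol pair leaves no part of the TEAE window without medication tabulation. The SAP pair leaves the last 98 days.

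**Step 3: early stoppers.** With a last dose at Week 84 (Day 589), TEAEs count to Day 589 + 98 = Day 687. The gap is again 98 days, and it is shorter only if the participant's study period ends sooner.

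**Step 4: does the treatment-period wording close the gap?** SAP 1.1 runs the treatment period to Week 108, which is 757 − 743 = 14 days past the last dose, and SAP 2.3.1 also counts exposure to last dose + 14 days. The definition of concomitant still stops at the last dose, so a drug first given in those 14 days lies inside counted exposure but outside the definition. Even if the table were run to Week 108, 841 − 757 = 84 days would remain.

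**Step 5: classify a drug first given after the last extension dose.** It is not prior, because it was not stopped before the core study. It is not concomitant, because it was not given by the last extension dose. The visible text defines no other category.

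**Step 6: how many participants?** Protocol 6.2 expects fewer than 10% to need treatment escalation, citing 12 flares in 120 patients (12/120 = 10%). 206 × 0.10 = 20.6, so fewer than about 21. For illustration only, 5% would be 10.3 and 2% would be 4.1. None of these is a count of drugs first started after the last dose, which the documents do not give.

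**The case against.** The strongest reply is that the gap is narrow and partly deliberate. Much of that stands, and it rules out several stronger readings that a reader might infer.

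- **That escape drugs will appear in no table at all.** Not established. Post therapies are named in headings, and their date imputation is deferred to a programming specification that is not among the documents. The text supports only that no table is defined in the visible SAP.
- **That 98 of a completer's 421 TEAE days (23%) lack medication coverage.** This is a calendar fraction. Any drug given at least once by the last dose is tabulated even if it continues into follow-up. Only drugs first given afterwards are missed.
- **That about 20 participants are affected.** The under-10% figure covers any escalation, including a steroid increase. Table 6-2 makes stopping case-by-case for DMARD changes and for prednisone above 10 mg, so some escalations happen while dosing continues and are captured.
- **That the 600 mg arm is distorted more.** Protocol 6.1.3 sends all core non-responders to 600 mg, but core 600 mg responders also stay there. Non-response means missing an improvement threshold, not worsening. No document says these participants need more escape treatment.
- **That follow-up events are wrongly charged to iscalimab.** Including them is a stated choice. Protocol 12.4.3 keeps all data regardless of intercurrent events, and Protocol 4.2 justifies 14 weeks by residual exposure. Treatment-related events are summarised separately.

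None of this answers the core point. The SAP states a rule that departs from Protocol 12.3, does not declare it, and leaves newly started follow-up drugs uncategorised. Summaries of treatment-related events do not show co-treatment.

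**Conclusion.** The concern holds as a mismatch of windows and an undeclared departure from the protocol. For up to 98 days after the last dose (Week 106 to Week 120 for completers), TEAEs are tabulated by dose but drugs first given in that period are not, as far as the visible SAP text goes. The mismatch should be corrected because escape immunosuppression is tied to stopping study drug and bears directly on how infection events are read.

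The effect on the results cannot be sized from the documents. Fewer than about 21 of 206 is an upper bound for any escalation, and imbalance between arms is a possibility, not a documented fact. The conclusion assumes that no post-therapy table is defined in material not available here, and that participants are followed for the full 98 days; where follow-up ends sooner, the gap shrinks with it.

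**What to change.** In SAP 2.3.2, restore the Protocol 12.3 end point: concomitant means given at least once from the first extension dose to the date of the last study visit. Tabulate by treatment group in two columns: on treatment (given on or before the last dose) and post-treatment (first given after the last dose). Alternatively, keep the SAP window, and declare and justify the departure in SAP Section 3.

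The last study visit is the better end point than last dose + 98 days. It is what the protocol says, and it can fall later, since Table 6-2 keeps some participants who stop study drug on the visit schedule.

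Optionally, in the adverse event listing, flag TEAEs that start on or after first use of a new systemic immunosuppressant or biologic begun after the last dose. The flag should not cover every Table 6-2 entry, because that table also lists antihistamines, antidepressants and live vaccines.

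The cost is one extra table column and, if adopted, one listing flag. No new data are needed: Table 8-1 records concomitant medication at Weeks 112 and 120, and Protocol 9.1.1 asks for new and concomitant treatments after discontinuation.

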2.4 Safety analyses

All safety endpoints (i.e., adverse events, laboratory data, and vital signs in extension study will be summarized by treatment for all subjects of the safety set.

Adverse events (AEs)

All adverse events in extension study are summarized based on treatment emergent only. The definition for "treatment emergent" is as below:

TEAE includes all events up to the last dose date plus 14 weeks (98 days) or the end of the entire study period (including the safety follow-up period), whichever occurred earlier. A listing of all adverse events during the study will be produced, with those defined as TEAE for the study treatment period with "treatment emergent" flag displayed.

The number and percentage of patients with treatment emergent adverse event (TEAE) will be summarized for the following:

- by treatment, primary system organ class and preferred term
- by treatment, primary system organ class, preferred term and maximum severity
- by treatment, Standardized MedDRA Query (SMQ) and preferred term.

Summaries will also be provided for study treatment related adverse events, serious adverse events, treatment related serious adverse events, deaths, and adverse events leading to permanent discontinuation of study-drug.

If a particular AE 'severity' is missing, this variable will be listed as missing and treated as missing in summaries. If a subject reported more than one adverse event with the same preferred term, the adverse event with the greatest severity will be presented. If a subject reported more than one adverse event within the same primary system organ class, the subject will be counted only once with the greatest severity at the system organ class level, where applicable.

The most common adverse events reported ($\geq 5\%$ in any group for each preferred term in the table by PT or $\geq 5\%$ in any group for each SMQ table) will be presented in descending frequency according to its incidence in all subjects starting from the most common event.

